5.5. Dose Justification

- The dose of rhEPO in this study will be the stable doses ($\leq 50\%$ change in 4-weekly dose) administered for at least 8 weeks prior to and including the screening period.
- The goal of the starting doses of daprodustat in this study is to maintain Hgb levels achieved on the prior rhEPO dose so that, on average, there is no change from baseline Hgb. Starting doses of 1, 2 or 4 mg of daprodustat are estimated to maintain Hgb levels observed with participant's prior rhEPO therapy based on population dose-response longitudinal modelling of Hgb data collected across the Phase 2 program (GlaxoSmithKline Document Number [2015N248947_00](#), 2016).

6. STUDY POPULATION

Prospective approval of protocol deviations to recruitment and enrolment criteria, also known as protocol waivers or exemptions, is not permitted.

6.1. Inclusion Criteria

Participants are eligible to be included in the study only if all the following criteria apply:

Age

1. Participant must be at least 18 years of age inclusive, at the time of signing the informed consent.

Type of Participant and Disease Characteristics

2. Participants who are Stage 3, 4 or 5 CKD (confirmed at Week -4 only) defined by eGFR using the CKD Epidemiology Collaboration (CKD-EPI) formula ([Levey, 2009](#)). See the Study Reference Manual (SRM) for details on calculation.

3. Participants who are currently treated with stable doses ($\leq 50\%$ change in 4-weekly dose) for at least 8 weeks prior to and including the screening period, of rhEPO (i.e., epoetin alfa or darbepoetin alfa).
4. Participants with Hgb levels between 9.0 and 11.5 g/dL, inclusive, who meet the Hgb stability criteria as outlined in Section 6.2.1.
5. Participants may be on stable maintenance oral iron supplementation ($<50\%$ change in overall dose and compliance of 80% of prescribed doses in the 4 weeks prior to and including the screening period). If participants have been on IV iron, then participants will not have received IV iron for 8 weeks prior to the Day 1 visit.

Sex

6. Male or female

a. Female participants:

A female participant is eligible to participate if she is not pregnant (see [Appendix 7](#)), not breastfeeding, and at least one of the following conditions applies:

- (i) Not a woman of childbearing potential (WOCBP) as defined in [Appendix 7](#)

OR

- (ii) A WOCBP who agrees to follow the contraceptive guidance in [Appendix 7](#) during the treatment period to the follow-up visit.

Informed Consent

7. Capable of giving signed informed consent as described in [Appendix 5](#) which includes compliance with the requirements and restrictions listed in the informed consent form (ICF) and in this protocol.

6.2. Exclusion Criteria

Participants are excluded from the study if any of the following criteria apply:

Medical Conditions

1. On dialysis or clinical evidence of impending need to initiate dialysis within 90 days after study start (i.e., Day 1).
2. Planned kidney transplant within 3 months after study start.
3. A positive test for HIV antibody.

Prior/Concomitant Therapy

4. History of severe allergic or anaphylactic reactions or hypersensitivity to excipients in the investigational products (see Daprodustat IB for list of excipients).
5. Use of any prescription or non-prescription drugs or dietary supplements that are prohibited from screening until the end of Treatment Period 2 (see Section 7.7.2).
6. Planned or current administration of Mircera (methoxy PEG-epoetin beta).

Prior/Concurrent Clinical Study Experience

7. The participant has participated in a clinical trial and has received an experimental investigational product within the prior 30 days or 5 half lives, whichever is longer, from screening through Day 1.

Diagnostic assessments

8. At or below the lower limit of the reference range at screening for Vitamin B₁₂ (may rescreen in a minimum of 8 weeks).
9. Ferritin outside the range between 100 and 500 ng/mL, inclusive, at screening.
10. Transferrin saturation (TSAT) outside the range between 15% and 40%, inclusive, at Screening.
11. Folate < 2.0 ng/mL (4.5 nmol/L; may rescreen in a minimum of 8 weeks) at screening.
12. High sensitivity C-reactive protein (hsCRP) ≥ 20 µg/mL at screening.

Other Exclusions

13. Myocardial infarction or acute coronary syndrome: ≤ 8 weeks prior to screening through Day 1.
14. Hospitalization for greater than 24 hours: ≤ 8 weeks prior to screening through Day 1
15. Stroke or transient ischemic attack ≤ 8 weeks prior to screening through Day 1.
16. Class IV heart failure, as defined by the New York Heart Association (NYHA) functional classification system.
17. Current uncontrolled hypertension as determined by the investigator.
18. QT interval corrected for heart rate using Bazett's formula (**QTcB**): QTcB > 500 msec, or QTcB > 530 msec in participants with Bundle Branch Block. There is no QTc exclusion for participants with a predominantly paced rhythm.
19. Active chronic inflammatory disease that could impact erythropoiesis. A partial list can be found in the Study Reference Manual (SRM).
20. History of bone marrow aplasia or pure red cell aplasia.
21. Conditions, other than anemia associated with chronic kidney disease, which can affect erythropoiesis. A partial list can be found in the SRM.
22. Evidence of actively bleeding gastric, duodenal, or esophageal ulcer disease OR clinically significant GI bleeding from ≤ 4 weeks prior to screening through Day 1.
23. Liver disease (any of the following):
 - Alanine transaminase (ALT) > 2x upper limit of normal (ULN; screening only)
 - Bilirubin > 1.5x ULN (screening only)
NOTE: Isolated bilirubin > 1.5 x ULN is acceptable if bilirubin is fractionated and direct bilirubin < 35%

- Current or chronic history of liver disease or known hepatic or biliary abnormalities (with the exception of Gilbert's syndrome or asymptomatic gallstones).
24. Major surgery (excluding vascular access surgery) within the 8 weeks prior to screening through Day 1 or planned during the study.
 25. Blood transfusion within 8 weeks prior to screening through Day 1, or an anticipated need for blood transfusion during the study.
 26. Clinical evidence of an acute infection, or history of infection requiring IV antibiotic therapy from 4 weeks prior to screening through Day 1.
NOTE: Prophylactic antibiotics are allowed.
 27. History of malignancy within the two years prior to screening through Day 1 or currently receiving treatment for cancer, with the exception of localized squamous cell or basal cell carcinoma of the skin definitively treated 12 weeks prior to Day 1.
 28. Any other condition, clinical or laboratory abnormality, or examination finding that the investigator considers would put the participant at unacceptable risk, which may affect study compliance or prevent understanding of the aims or investigational procedures or possible consequences of the study.

[figure not shown]
6.2.1. Hgb Stability Criteria

Entry into the study requires a stable Hgb between **9.0 - 11.5 g/dL**.

- This criterion is assessed from an average of **three** Hgb values obtained via a validated point-of-care device to measure Hgb (HemoCue) on site during the screening period at Week -4, Week -2 and on Day 1.
- The Hgb stability assessment is the difference between the maximum and minimum values of the three Hgb measurements obtained between Week -4 and Day 1.

A decision algorithm for Hgb stability is shown in [Figure 3](#).

Figure 3 Hgb Stability Criteria

6.3. Lifestyle Restrictions

No lifestyle restrictions are required.

6.4. Screen Failures

Screen failures are defined as participants who consent to participate in the clinical study but are not subsequently randomized. A minimal set of screen failure information is required to ensure transparent reporting of screen failure participants to meet the Consolidated Standards of Reporting Trials (CONSORT) publishing requirements and to respond to queries from regulatory authorities. Minimal information includes demography, screen failure details, eligibility criteria, and any serious adverse events (SAEs).

Individuals who do not meet the criteria for participation in this study (screen failure) may be rescreened.

7. TREATMENTS

Study treatment is defined as any investigational treatment(s), marketed product(s), placebo, or medical device(s) intended to be administered to a study participant according to the study protocol.

Participants at study entry will discontinue their rhEPO therapy (i.e., epoetin alfa or darbepoetin alfa) prior to randomization so that the randomization date (Day 1) should coincide, as closely as possible, with the date of the next scheduled rhEPO administration. Examples of switching are provided in the SRM.

7.1. Treatments Administered

Study Treatment Name:	Daprodustat	rhEPO (epoetin alfa OR darbepoetin alfa)	⁵⁷ Fe	⁵⁸ Fe
Dosage formulation:	Tablet	Solution for injection	⁵⁷ FeSO ₄ Oral solution	⁵⁸ FeSO ₄ / ⁵⁶ FeSO ₄ Oral solution
Unit dose strength(s)/ Dosage level(s):	1 mg, 2 mg, 4 mg tablet strengths/1 mg, 2 mg, 4 mg dosage levels	rhEPO is commercially available in various single-dose vials and single-dose prefilled syringes	⁵⁷ FeSO ₄ (containing 10 mg of ⁵⁷ Fe) 10 mg total dose of Fe	⁵⁸ FeSO ₄ (containing 3 mg of ⁵⁸ Fe) ⁵⁶ FeSO ₄ (containing 7 mg of ⁵⁶ Fe) 10 mg total dose of Fe
Route of Administration	Oral	Subcutaneous injection	Oral	Oral
Dosing instructions:	1 tablet to be taken daily without regard for food	As per product labelling	Full dosing instructions can be found in the SRM	Full dosing instructions can be found in the SRM
Packaging and Labeling	Study Treatment will be provided in a bottle. Each bottle will be labeled as required per country requirement.	As per product labelling	N/A	N/A
Manufacturer	GSK	Amgen	Formulated by extemporaneous compounding	Formulated by extemporaneous compounding

7.1.1. Daprodustat Dosing Information

Doses of daprodustat to be administered are based on the rhEPO dose at randomization (Day 1) as described in [Table 2](#).

Table 2 Daprodustat Doses

Darbepoetin alfa ($\mu\text{g}/4$ wk SC/IV)	Epoetin alfa (convert SC to IV U/week) ¹	Daprodustat dose (mg, once daily)
20 to 30	1500 to 2000	1
>30 to 300	>2000 to <20000	2
>300	≥ 20000	4

¹ Standardized rhEPO IV dose (U/week) = $161/113 \times (\text{epoetin SC dose (units)/frequency})$

7.1.2. rhEPO Dosing Information

Participants are required to be currently treated with stable doses ($\leq 50\%$ change in 4-weekly dose) of rhEPO for at least 8 weeks prior to and including the screening period. The dose of rhEPO to be administered during the study as randomized study treatment will be the rhEPO dose at randomization (Day 1). This dose is to be administered whether a participant is randomized to rhEPO on Treatment Period 1, or is switching back to rhEPO following 4 weeks of administration of daprodustat on Treatment Period 2.

7.1.3. ⁵⁷Fe Dosing Information

An oral solution will be administered containing 10 mg of ⁵⁷Fe as ferrous sulfate. Exact doses will be measured, calculated, and captured for each individual participant. The solution is to be taken following an overnight fast. Further details will be outlined in the compounding document and SRM.

7.1.4. ⁵⁸Fe Dosing Information

An oral solution will be administered containing 3 mg of ⁵⁸Fe as ferrous sulfate with 7 mg of ⁵⁶Fe as ferrous sulfate (natural abundance Fe). Exact doses will be measured, calculated, and captured for each individual participant. The solutions are to be taken following an overnight fast. Further details will be outlined in the compounding document and SRM.

7.2. Dose Modification

No dosage modification is anticipated in this study. However, if it becomes medically necessary to adjust the dose of either rhEPO or daprodustat, the participant is to be withdrawn from the study.

7.3. Method of Treatment Assignment

All participants will be centrally randomized using an Interactive Voice/Web Response System (IVRS/IWRS). Before the study is initiated, the telephone number and call-in directions for the IVRS and/or the log in information & directions for the IWRS will be provided to each site.

7.4. Blinding

This is an open-label study; potential bias will be reduced by using central randomization. Further, fractional iron absorption is an objective endpoint, such that participant knowledge of the treatment received is unlikely to affect the results.

7.5. Preparation/Handling/Storage/Accountability

- The investigator or designee must confirm appropriate temperature conditions have been maintained during transit for all study treatment received and any discrepancies are reported and resolved before use of the study treatment.
- Only participants enrolled in the study may receive study treatment and only authorized site staff may supply or administer study treatment. All study treatments must be stored in a secure, environmentally controlled, and monitored (manual or automated) area in accordance with the labeled storage conditions with access limited to the investigator and authorized site staff.
- The investigator, institution, or the head of the medical institution (where applicable) is responsible for study treatment accountability, reconciliation, and record maintenance (i.e., receipt, reconciliation, and final disposition records).
- Further guidance and information for the final disposition of unused study treatment are provided in the SRM.
- Under normal conditions of handling and administration, study treatment is not expected to pose significant safety risks to site staff. Take adequate precautions to avoid direct eye or skin contact and the generation of aerosols or mists. In the case of unintentional occupational exposure notify the monitor, Medical Monitor and/or GSK study contact.
- A Material Safety Data Sheet (MSDS)/equivalent document describing occupational hazards and recommended handling precautions either will be provided to the investigator, where this is required by local laws, or is available upon request from GSK.

7.6. Treatment Compliance

- When the individual dose for a participant is prepared from a bulk supply, the preparation of the dose will be confirmed by a second member of the study site staff.
- When participants are dosed at the site, they will receive study treatment directly from the investigator or designee, under medical supervision. The date and time of each dose administered in the clinic will be recorded in the source documents. The dose of study treatment and study participant identification will be confirmed at the time of dosing by a member of the study site staff other than the person administering the study treatment.
- When participants self-administer study treatment(s) at home, compliance will be assessed through querying the participant during the site visits and documented in the source documents and eCRF. A record of the study treatment dispensed to and taken by each participant must be maintained and reconciled with study treatment and compliance records. Treatment start and stop dates, including dates for treatment delays and/or dose reductions will also be recorded in the eCRF.

7.7. Concomitant Therapy

Any medication or vaccine (including over-the-counter or prescription medicines, vitamins, and/or herbal supplements) that the participant is receiving at the time of enrolment or receives during the study must be recorded along with:

- reason for use
- dates of administration including start and end dates
- dosage information including dose and frequency

The Medical Monitor should be contacted if there are any questions regarding concomitant or prior therapy.

7.7.1. Permitted Medications and Non-Drug Therapies

Unless specified as a prohibited medication in Section 7.7.2, all concomitant medications should be considered permitted provided they are not contraindicated for the individual participant concerned.

Participants are to be advised to maintain use of the following medications at a consistent dosage and frequency:

- Oral iron supplementation (except ferric citrate, which is prohibited; see Section 7.7.2)
- Acid-reducing agents (e.g., H₂ receptor antagonists, proton pump inhibitors, antacids)

7.7.2. Prohibited Medications and Non-Drug Therapies

Use of any of the following prescription drugs from screening (Week -4) until the end of Treatment Period 2 is prohibited and will constitute a protocol deviation:

- Strong inhibitors of CYP2C8 (e.g., gemfibrozil, high dose clopidogrel [300 mg])
- Strong inducers of CYP2C8 (e.g., rifampin/rifampicin)
- The oral iron supplement ferric citrate
- Intravenous administration of iron
- Any rhEPO other than epoetin alfa or darbepoetin alfa

7.7.3. Standard of Care

During the study, investigators are expected to monitor the participant's overall clinical status to ensure standards of care are met to enable consistency of practice with KDIGO guidelines or local equivalent.

7.8. Treatment after the End of the Study

Participants will not receive any additional treatment from GSK after completion of the study because the indication being studied is not life threatening or seriously debilitating and other treatment options are available.

The investigator is responsible for ensuring that consideration has been given to the post-study care of the participant's medical condition.

8. DISCONTINUATION CRITERIA

8.1. Discontinuation of Study Treatment

Participants that discontinue study treatment should be withdrawn from the study. See Section 8.2 for a description of withdrawal procedures.

[figure not shown]
8.1.1. Liver Chemistry Stopping Criteria

Liver chemistry stopping and increased monitoring criteria have been designed to assure participant safety and evaluate liver event etiology.

Discontinuation of study treatment for abnormal liver tests is required when:

- a participant meets one of the conditions outlined in [Figure 4](#)
OR
- when in the presence of abnormal liver chemistries not meeting protocol-specified stopping rules, the investigator believes study treatment discontinuation is in the best interest of the participant.

Figure 4 Phase III-IV Liver Chemistry Stopping and Increased Monitoring Algorithm

Liver Safety Required Actions and Follow up Assessments Section can be found in [Appendix 2](#).

8.2. Withdrawal from the Study

- A participant may withdraw from the study at any time at his/her own request or may be withdrawn at any time at the discretion of the investigator for safety, behavioral, compliance or administrative reasons.
- If the participant withdraws consent for disclosure of future information, the sponsor may retain and continue to use any data collected before such a withdrawal of consent.
- If a participant withdraws from the study, he/she may request destruction of any samples taken and not tested, and the investigator must document this in the site study records.
- Participants that withdraw/are withdrawn from the study treatment are encouraged to attend the follow-up visit 14 ± 3 days following discontinuation of study treatment. Assessments to be conducted are listed in the SoA (Section 2).

8.2.1. Criteria for Permanent Discontinuation from Study Treatment and Early Withdrawal

Participants must **permanently discontinue study treatment** and be withdrawn from the study for the following reasons:

- Meets Hgb stopping criteria (See Section 8.2.1.1)
- Meets iron stopping criteria (See Section 8.2.1.2)
- If it becomes medically necessary to adjust the dose of either rhEPO or daprodustat
- Receives a blood transfusion
- Receives a kidney transplant
- Becomes pregnant or intends to become pregnant during the study
- Active GI bleeding
- Diagnosis of cancer, with the exception of squamous cell or basal cell carcinoma
- Liver chemistry abnormalities exceeding the threshold criteria (See Section 8.1.1)
- Use of prohibited medication (See Section 7.7.2)
- Active chronic inflammatory disease that could impact erythropoiesis
- Any new diagnosis of hematological disease including those affecting platelets, white or red blood cells, coagulation disorders, or any other cause of anemia of chronic disease other than renal disease

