9.2.4. Adverse Events of Special Interest (AESI)

Adverse Events of Special Interest (AESI) have been identified based on non-clinical studies with daprodustat, clinical experience with rhEPOs, and current information regarding HIF-regulated pathways in mediating hypoxia-associated pathophysiology. The currently identified AESI for daprodustat are as follows:

- Thrombosis and/or tissue ischemia secondary to excessive erythropoiesis
- Death, MI, stroke, heart failure, venous thromboembolism, thrombosis of vascular access
- Cardiomyopathy
- Pulmonary artery hypertension
- Cancer-related mortality and tumor progression and recurrence
- Esophageal and gastric erosions
- Proliferative retinopathy, macular edema, choroidal neovascularization
- Exacerbation of rheumatoid arthritis
- Worsening of hypertension

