
Cancer-related mortality and tumor progression and recurrence
	
Marketed rhEPOs have been associated with increased risk of cancer related morbidity and mortality when used in patients with cancer.
 
Administration of 60 mg/kg daprodustat to mice caused minimal increases in circulating VEGF while significant EPO increases were observed.
 
In clinical studies with daprodustat up to 4 weeks duration, a dose-ordered increase in VEGF plasma concentrations, an angiogenic factor that has been implicated in tumor growth, was observed at doses ranging from 10 to 150 mg. In clinical studies up to 24 weeks duration at doses up to 25 mg, changes in VEGF plasma concentrations were variable but similar relative to control.
 
Integrated AE data [including 2 global phase 2b studies (24-week treatment duration) and 2 Japanese phase 3 studies (52-week treatment duration)]: No meaningful difference was seen between treatment groups in the occurrence of this AESI: [8/688 (1.1%) daprodustat vs. 4/404 (0.9%) rhEPO; 1.14 relative risk (95% confidence interval: 0.31, 4.28)].
 
Clinical experience to date is not yet sufficient to substantiate or refute this as a safety concern for daprodustat.
	
 • Specific eligibility criteria related to personal history of malignancy are outlined in Section 6.2. • Stopping criteria for participants with treatment emergent malignancy are outlined in Section 8.2.1. • Monitoring of emerging safety data by an internal GSK Safety Review Team.

Potential Risk of Clinical Significance	Summary of Data/Rationale for Risk	Mitigation Strategy

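### The mandatory cancer stop in Protocol 8.2.1 exempts squamous cell carcinoma of any site or stage, which is looser than the matching entry exclusion

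*Protocol*

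**What the plan says.** Section 8.2.1 of the protocol lists reasons for which a participant must permanently stop study treatment and leave the study. One is "Diagnosis of cancer, with the exception of squamous cell or basal cell carcinoma".

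The entry rule on malignancy, Exclusion 27 in Section 6.2, has a corresponding exemption with more conditions: "with the exception of localized squamous cell or basal cell carcinoma of the skin definitively treated 12 weeks prior to Day 1".

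The risk table in Appendix 12.3 covers cancer-related mortality and tumor progression and recurrence. Its mitigation column refers the reader back to the stopping rule: "Stopping criteria for participants with treatment emergent malignancy are outlined in Section 8.2.1". The rationale column says "Marketed rhEPOs have been associated with increased risk of cancer related morbidity and mortality when used in patients with cancer". It reports events of this type as "8/688 (1.1%) daprodustat vs. 4/404 (0.9%) rhEPO" and concludes "Clinical experience to date is not yet sufficient to substantiate or refute this as a safety concern for daprodustat". The same risk, "Cancer-related mortality and tumor progression and recurrence", is an adverse event of special interest in Section 9.2.4.

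**The concern.** Squamous cell carcinoma is a histological type, not a site. Exclusion 27 deals with this by adding a stage limit (localized) and a site limit (skin). The on-study item in 8.2.1 has neither. As the text stands, someone who could not enter with a squamous carcinoma of an internal organ, or with a skin carcinoma that is not localized, need not leave on receiving that diagnosis during treatment.

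What is at stake is participant safety rather than inference. Appendix 12.3 cites 8.2.1 as the stopping rule for on-treatment malignancy, and no other section supplies the missing limits. The protocol treats the cancer question as open for daprodustat and as an established risk for rhEPO in patients who have cancer. The rule that closes off exposure should therefore not be looser than the rule for entry.

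**Working it through.** **Text comparison.**

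| Limit on the exempt carcinoma | Exclusion 27 (Section 6.2) | Stop item (Section 8.2.1) |
|---|---|---|
| Localized | Yes | No |
| Of the skin | Yes | No |
| Definitively treated 12 weeks before Day 1 | Yes | No |

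The third limit is an entry condition. No lesion first diagnosed on study could meet it, so its absence from 8.2.1 is correct. The two limits that matter are localized and of the skin.

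**Could another provision make the stop mandatory?**

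- Section 8.2 lets the investigator withdraw a participant for safety. This is permissive.
- Section 9 requires immediate safety concerns to be discussed at once with the sponsor, to decide whether the participant continues or stops. This prescribes a decision, not its outcome.
- Section 9.2.1 requires SAE reporting within 24 hours, and Appendix 12.6 gives invasive or malignant cancers as examples of events usually considered serious. This informs the sponsor.
- Sections 7.2 and 8.2.1 require withdrawal if a dose change becomes medically necessary. That applies only once someone judges a change necessary.
- The last item in 8.2.1 covers new hematological disease and "any other cause of anemia of chronic disease other than renal disease". Some carcinomas could be brought under it, but not every one clearly is.

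None of these requires withdrawal for every case that the exemption lets through.

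**Rough expected count.** The protocol gives no rate of new cancer diagnoses. The nearest figure is the event count in Appendix 12.3, from studies of 24 and 52 weeks.

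- Source figures: 8/688 = 1.16% and 4/404 = 0.99%. The table prints 1.1% and 0.9%; the small difference has no effect here.
- Pooled: (8 + 4)/(688 + 404) = 12/1092 = 1.10%.
- Twelve participants over the source follow-up: 12 × 0.01099 = 0.132 events.
- Scaled to 8 weeks of treatment (2 × 28 days) if all source follow-up was 52 weeks: 0.132 × 8/52 = 0.020.
- Scaled to 8 weeks if all source follow-up was 24 weeks: 0.132 × 8/24 = 0.044.

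The result is about 0.02 to 0.04 events of any cancer type. The share that is squamous and either outside the skin or not localized is smaller, and the documents do not give it.

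**Exposure.** Each participant takes daprodustat in one 28-day period only. In the other period the participant receives the rhEPO used before the study, at the dose held at randomization (Sections 5.1 and 7.1.2). Continued treatment that the trial itself adds is therefore at most 28 days of daprodustat.

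**The case against.** The best defense is that nobody would read the item this way. Squamous cell and basal cell carcinoma are named as a pair in Exclusion 27 with the skin limit attached, and 8.2.1 reads naturally as shorthand for it. A site that found an internal squamous cancer would have to treat it as exempt, report it as serious, discuss it with the sponsor and still continue dosing. Section 7.7.3 also expects standards of care to be maintained. This largely stands: the intent is probably skin carcinoma, and a case passing unnoticed is implausible. It does not repair the rule. Reading in the skin limit still leaves out the stage limit, and the other provisions leave to judgment a stop that 8.2.1 is meant to make mandatory.

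The second defense is rarity, and it also stands. The proxy is loose as well: the counts are for an event category named for cancer mortality, progression and recurrence, not for new diagnoses. Rarity limits the weight of the point but does not make the wording right.

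A reader might also infer that 8.2.1 ought to mirror the exclusions throughout, and so should add the start of dialysis beside kidney transplant. The documents do not support that. Myocardial infarction, stroke, Class IV heart failure and uncontrolled hypertension are also entry exclusions with no matching stop. The consequences of dialysis most likely to disturb iron absorption are already stops: intravenous iron (Sections 7.7.2 and 8.2.1), dose adjustment and transfusion (8.2.1), and a change of oral iron dose (8.2.1.2). Exclusion 1 removes those with impending need within 90 days, which runs past the Day 70 visit.

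**Conclusion.** The point holds as a minor fault of safety wording. Read literally, the cancer stop in 8.2.1 does not require withdrawal for a new squamous cell carcinoma that is outside the skin or not localized, although Exclusion 27 would have barred such a participant and Appendix 12.3 relies on 8.2.1 for this situation.

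The expected impact is very small. The range of 0.02 to 0.04 assumes a constant event rate, a rate in this trial like that in the source studies, the event count as a stand-in for new diagnoses, and 12 participants completing 8 weeks. It scales in proportion if more are randomized to reach 12 evaluable.

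Two stronger readings should be resisted. One is that participants with such cancers would in practice be kept on treatment; the investigator and sponsor provisions make that unlikely. The other is that all 56 days of study treatment are at stake; the rhEPO period continues the participant's own prior therapy. Nothing here bears on the sample size, the model or the primary comparison.

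**What to change.** In the 8.2.1 cancer item, insert *localized* before squamous cell and *of the skin* after carcinoma. Do not carry over the 12-week treatment condition from Exclusion 27.

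The cost is a few words and, because Appendix 12.5 requires ethics approval of amendments, a place in the next amendment. In the unlikely event of a case, one participant would be withdrawn and, if necessary, another enrolled to keep at least 12 in the Evaluable Population. No analysis set, endpoint or model changes.
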